PROTOCOL TITLE:

TRAGUS STIMULATION TO PREVENT ATRIAL FIBRILLATION AFTER CARDIAC SURGERY: THE TRAP-AF STUDY

PI: [name]

Co-I(s): [name], [name]; [name] MD, [name] MD; [name] PhD; [name], [name], [name], [name], [name], [name], [name]

FUNDING: INTERNAL

SPONSOR: NONE

TYPE OF RESEARCH: CLINICAL TRIAL

INTERVENTION: TRANSCUTANEOUS LOW-LEVEL TRAGUS STIMULATION (LLTS)

MANUFACTURER OF INTERVENTION: NOT APPLICABLE

IND OR IDE # NOT APPLICABLE

STUDY SUMMARY

TITLE	Tragus Stimulation to Prevent Atrial Fibrillation after Cardiac Surgery
SHORT TITLE	The TraP-AF Study
PROTOCOL NUMBER	IRB17-1365
METHODOLOGY	Single-blind clinical trial
STUDY DURATION	1 year
STUDY CENTER(S)	Single-center
OBJECTIVES	To compare the effectiveness of transcutaneous low-level tragus stimulation (LLTS) of the auricular branch of the vagus nerve versus sham in the prevention of postoperative atrial fibrillation (POAF) after cardiac surgery.
NUMBER OF SUBJECTS	80 patients
DIAGNOSIS AND MAIN INCLUSION CRITERIA	
Patients undergoing coronary artery bypass graft (CABG) surgery and/or valve surgery who are 18 years of age or older at the University of Chicago will be eligible for evaluation for inclusion into this study. Exclusion criteria include:
 
 1) Prior history of persistent or permanent atrial fibrillation (AF) as determined by detailed chart review 2) Emergency cases 3) Pregnant patients 4) Patients undergoing the following procedures: heart transplant, pulmonary thromboendarterectomy, isolated aortic arch procedures, ventricular assist device insertion, extracorporeal membrane oxygenation insertion, and surgical AF ablation
STUDY PRODUCT	Transcutaneous low-level tragus stimulation (LLTS) is a completely noninvasive technique which utilizes an FDA approved transcutaneous electrical nerve stimulation (TENS) device (Parasym, Parasym Health). This device consists of a battery-powered, programmable transcutaneous electrical nerve stimulation (TENS) unit and a pair of stimulation electrodes that can be clipped to the tragus of the external ear in order to stimulate the auricular branch of the vagus nerve.
DURATION OF ADMINISTRATION	LLTS will be administered continuously for 48 hours, beginning immediately after surgery. The stimulator will be shifted from one ear to the other every 4 hours.

REFERENCE THERAPY	The reference therapy will be a sham control group; i.e., patients on whom an LLTS device with a non-functioning electrode will be applied and in whom therapy will not be delivered.
STATISTICAL METHODOLOGY	Traditional statistical methods will be employed. The student's T-test will be used for continuous comparisons. Fisher's exact or the Chi-square test will be applied for dichotomous variables. Time to endpoint analysis will be performed using the Kaplan-Meier method.

LIST OF ABBREVIATIONS

AAD	ANTIARRHYTHMIC DRUG THERAPY
ACE-I	ANGIOTENSIN-CONVERTING ENZYME INHIBITOR
AF	ATRIAL FIBRILLATION
ARB	ANGIOTENSIN RECEPTOR BLOCKER
BB	BETA-BLOCKER
CABG	CORONARY ARTERY BYPASS GRAFT
CRT	CARDIAC RESYNCHRONIZATION THERAPY
FDA	FOOD AND DRUG ADMINISTRATION
GDMT	GOAL-DIRECTED MEDICAL THERAPY
HF	HEART FAILURE
ICD	IMPLANTABLE CARDIOVERTER-DEFIBRILLATOR
IRB	INSTITUTIONAL REVIEW BOARD
LBBB	LEFT BUNDLE-BRANCH BLOCK
LV	LEFT VENTRICULAR
LLTS	LOW-LEVEL TRAGUS STIMULATION
LVEF	LEFT VENTRICULAR EJECTION FRACTION
NYHA	NEW YORK HEART ASSOCIATION
POAF	POSTOPERATIVE ATRIAL FIBRILLATION
POD	POSTOPERATIVE DAY
RA	RIGHT ATRIUM
RV	RIGHT VENTRICLE
SR	SINUS RHYTHM
TTE	TRANSTHORACIC ECHOCARDIOGRAM
UCMC	UNIVERSITY OF CHICAGO MEDICAL CENTER
UofC	UNIVERSITY OF CHICAGO
VT	VENTRICULAR TACHYCARDIA
VF	VENTRICULAR FIBRILLATION

1. INTRODUCTION

A. BACKGROUND AND RATIONALE

New-onset postoperative atrial fibrillation (POAF) commonly complicates cardiac surgery, affecting between 20 and 50% of patients,¹ with an even higher risk for patients undergoing combined coronary artery bypass graft (CABG) and/or valve replacement procedures.^{2,3} The spectrum of POAF varies from self-limited episodes to persistent AF requiring antiarrhythmic drug therapy (AAD) and cardioversion.

Overall, POAF portends significantly worse clinical outcomes, including an up to four-fold increased risk of stroke and doubling of both all-cause 30-day and 6 month mortality.⁴ In addition, POAF is independently associated with prolonged intensive care unit (ICU) stays, longer overall duration of hospitalization (extending length-of-stay by 2 to 5 days), and significantly increased costs by \$10,000-20,000, even during the index hospitalization.^{4,5} POAF usually occurs between 2 and 4 days after surgery, with a peak incidence on postoperative day 2.⁶ The pathogenesis of POAF in the cardiac surgical setting remains poorly understood, although there is data to suggest that autonomic imbalance during the post-operative period may play a key role for some patients.¹

Peripheral vagal nerve stimulation can alter central parasympathetic cardiac inputs, leading to reduced heart rate along with reduced dispersion of atrial effective refractory periods (AERPs), lowering the risk of AF.^{7,8} While direct vagal nerve stimulation has an established role in the treatment of intractable epilepsy and treatment-resistant depression,^{9,10} its application for POAF has been limited due to its invasive nature and increased risks.

Transcutaneous low-level tragus stimulation (LLTS), however, has recently emerged as a novel, entirely noninvasive means to achieve vagal nerve stimulation, which achieves anticholinergic and antiadrenergic effects.¹¹ The auricular branch of the vagus nerve localizes to the skin near the anterior protuberance of the outer ear, called the tragus. LLTS has been shown to significantly suppress AF inducibility, reduce overall AF duration, and reduce the production of inflammatory cytokines (i.e., TNF-alpha and C-reactive protein) in acute studies.¹²⁻¹⁵ Furthermore, it may have additional benefits in inducing autonomic remodeling, as well as reducing ventricular arrhythmia.¹⁶ The Parasym device delivers LLTS through the skin via the outer ear (see Appendix A, Figures 1-2). It has been used in a variety of medical treatments, including tinnitus, depression, anxiety, and rheumatoid arthritis. We seek to evaluate the role of LLTS in preventing POAF, reducing AF duration, reducing average length of stay, and reducing overall arrhythmia incidence after cardiac surgery.

B. OBJECTIVES

We hypothesize that:

- a. In patients undergoing cardiac surgery (i.e., CABG and/or valve surgery), new-onset POAF is common
- b. LLTS is a simple, noninvasive and effective means to reduce the incidence of POAF, reduce overall AF duration, and reduce incidence of significant ventricular arrhythmias (i.e., nonsustained or sustained VT/VF)
- c. Use of LLTS in the inpatient setting leads to reduced overall AF and reduced AF duration in the 30-day period after cardiac surgery

Specific aims:

Aim 1: To determine the overall rate of successful LLTS in the inpatient setting. Patients randomized to LLTS will undergo continuous stimulation for two inpatient days. Tolerance of LLTS versus sham will be assessed.

Aim 2: To assess the impact of LLTS on acute and short-term outcomes. Acute outcomes include the incidence of inpatient POAF during the index hospitalization, length of hospital stay, overall AF duration, and incidence of nonsustained or sustained VT/VF. Short-term outcomes include incidence of AF as assessed by 14-day monitor (i.e. Zio patch or CardioNet event monitor) upon discharge.

2. STUDY DESIGN

Study design: Single-blind study. Patients will be randomized, to LLTS versus sham procedure, and remain blinded to their treatment allocation. Both treatment options will utilize similar equipment, namely the use of alligator clips which will be placed on the tragus and earlobe of the right ear for patients (see Appendix A, Figure 2). The distinction is only that in patients assigned to LLTS, they will be initiated on therapy at the time of device placement.

Prior to cardiac surgery, the discomfort threshold of both left and right tragus stimulation will be determined for all participating patients. Intermittent electrode signals, or microcurrents, are delivered at 20 Hz with 200 μ sec pulse width with variable microampere (mA) output. The discomfort threshold is defined as the stimulation intensity in mA at which point patients experience discomfort. The stimulation intensity used in the study will be set just below the discomfort threshold, as established from prior work.¹⁵ The clip will then be placed on the patient's ear at the end of surgery. After surgery is completed, the clip will then be removed and replaced on the contralateral ear. Stimulation will then continue, one ear alternating with the other, every 4 hours for a total of 48 hours. It is possible that the threshold can change during the post-operative period. If the patient shows any sign of discomfort from stimulation, the intensity of stimulation will be reduced to a level at which signs of discomfort disappears.

Follow-up will be performed with 14-day event monitor (i.e. Zio patch or CardioNet event monitor) at the time of discharge.

Electrocardiography (i.e. ECG) will be performed pre-procedure and prior to hospital discharge. Echocardiography will be assessed prior to study initiation and when clinically available in follow-up.

Duration of study: 1 month

Primary endpoints: A combination of clinical and electrocardiographic endpoints will be prospectively studied. These include:

- **Clinical:** Primary clinical endpoint is time to inpatient AF (length of stay >5 days). Secondary endpoint is any occurrence of AF during 14 day post procedure monitoring.
- **Electrocardiographic:** Arrhythmia occurrence (i.e., AF, nonsustained VT, VT or VF requiring device therapy) will be documented throughout the study period

Primary safety endpoint: Procedure-related complications will be assessed prospectively both acutely and throughout the study period, including:

- **Procedure related:** pain, tragus site abrasion or bruising

Randomization scheme: Patients will be allocated to LLTS or sham in a 1:1 ratio at time of implant based on random number generator.

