6. STATISTICAL PLAN AND CONSIDERATIONS

Primary Outcome:

1. Time to the first episode of AF >30 seconds during inpatient admission or within 14-day monitoring period

- a. In hospital: full-disclosure telemetry
- b. Time to AF will be assessed by physicians blinded to randomization
- 2. Extended hospitalization of >5 days

Secondary Outcomes:

- 1. Overall AF burden, as assessed by 2 week monitor (CardioNet or Zio Patch) upon discharge
- 2. Inflammatory markers: C-reactive protein (ordered if clinically indicated)
- 3. Actionable AF: antiarrhythmic use (including rate-control meds), CDV, anticoagulation, use of inotropes for BP support during AF
- 4. Stroke or transient ischemic attack (TIA)
- 5. All cause of mortality

Sample size estimation:

Assuming a two-armed study with composite endpoint of occurrence of AF or >5 days hospitalization, whereby the treatment group will have 50% likelihood of the event occurring and a control group will have 20% likelihood of the event occurring, as well as a 10% dropout rate, we will be able to detect differences in 80 patients (40 in each arm). Under these assumptions and using two-sided Z-Test with unpooled variance to compare the changes between these two groups, we will have 80% power ($\alpha=0.05$) to detect a difference between the group proportions of 0.30. PASS software Version 15 (NCSS, LLC, Kaysville, UT) was used to calculate the statistical power.

Statistical methods:

Patients will be studied based on the randomization allocation. Patients who refuse to continue with study treatment (i.e. they refuse to wear ear clip) during time of therapy will be analyzed as intention-to-treat per allocation group. Fisher's exact or the Chi-Square test will be used for categorical variables, and continuous parameters will be compared by the two-tailed unpaired Student's t test and the F test for analysis of variance (ANOVA), as needed. Kaplan-Meier method will be used for computing the event free survival curves. Each strategy will be compared within this cohort of patients for its impact on percent incidence of POAF and length of stay. Multiple logistic regression and multiple regressions using the Cox proportional hazards model will be performed to determine the independent association of each of the demographic variables with clinical outcome.

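### Kaplan-Meier for time to inpatient AF: censoring AF-free patients at discharge overstates inpatient AF in both arms and distorts the arm difference in an unknown direction

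*Combined protocol and SAP*

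**What the plan says.** The protocol defines the AF endpoint in two ways.

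- Section 2 (Study Design): "Primary clinical endpoint is time to inpatient AF", with a stay of more than 5 days attached in parentheses. Post-discharge AF is placed lower: "Secondary endpoint is any occurrence of AF during 14 day post procedure monitoring".
- Section 6 (Primary Outcome): "Time to the first episode of AF >30 seconds during inpatient admission or within 14-day monitoring period", followed by a second item, "Extended hospitalization of >5 days". Here follow-up for AF continues after discharge.

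Aim 2 in Section 1.B also treats in-hospital AF separately: "Acute outcomes include the incidence of inpatient POAF during the index hospitalization".

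On method, the synopsis says "Time to endpoint analysis will be performed using the Kaplan-Meier method" and Section 6 says "Kaplan-Meier method will be used for computing the event free survival curves". Section 6 also names Cox regression, but to relate demographic variables to outcome. It says the strategies will be compared on the percentage with POAF and on length of stay, and it lists Fisher's exact or chi-square tests for categorical variables. Neither the synopsis nor Section 6 gives a censoring rule at discharge, a competing-risk method, or a rule for death before AF.

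**The concern.** For an inpatient-only endpoint, leaving hospital without AF is not incomplete follow-up. It settles the outcome: the patient did not have inpatient AF. In-hospital death without AF does the same. Kaplan-Meier recognises only events and censored observations. On the usual reading an AF-free patient is censored at discharge and is then treated as still liable to inpatient AF, at the rate seen in those who stay. Almost every AF-free patient is discharged, so this is the main feature of the data.

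Two things are at stake. The curve would show more inpatient AF than occurred, and would disagree with the percentage with POAF in the same report. The gap between the curves would also be distorted, because the error need not be the same size in both arms. The right-hand end of the curve is fragile as well: in simulations at 36 evaluable patients per arm, only about 0.3 to 3.6 patients per arm were still at risk at day 10.

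**Working it through.** **1. The plan's own figure.** Section 6 gives 50% v 20%, 80% power, two-sided alpha 0.05, unpooled variance and 10% dropout.

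n = (1.960 + 0.842)² × (0.5×0.5 + 0.2×0.8) / 0.30² = 35.76, so 36 per arm. Then 36/0.90 = 40 per arm, or 80 in total. This reproduces. It rests on a binary composite, so nothing below changes it. The text gives the 50% to treatment and the 20% to control. I take 50% as sham and 20% as LLTS, the hypothesised direction; N is the same either way.

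**2. Size of the overstatement in one arm.** The documents give no discharge times, so these counts are illustrative: 36 patients, 10 with AF by day 4, 22 discharged AF-free on day 5, 4 remaining, and one of those with AF on day 8.

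- Inpatient AF that occurred: 11/36 = 30.6%.
- 1−KM with censoring at discharge: 1 − (26/36)(3/4) = 45.8%.

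In general, let S be the proportion AF-free when discharges begin, d the fraction of those sent home at that point, and q the later inpatient AF risk among those who stay.

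- True incidence = (1−S) + S(1−d)q
- 1−KM = (1−S) + Sq
- Excess = S·d·q

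Check: (26/36)(22/26)(1/4) = 15.3 points = 45.8 − 30.6. The excess cannot be negative.

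**3. Direction for the arm difference.** The change in the difference (sham minus LLTS) is the sham excess minus the LLTS excess. Assume S = 0.50 for sham and 0.80 for LLTS, d = 22/26 in both arms, and q = 0.25 for sham.

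- Equal late risk (LLTS q = 0.25): 0.50×0.846×0.25 − 0.80×0.846×0.25 = 0.106 − 0.169 = −0.063. The difference shrinks.
- Effect persists (LLTS q = 0.25×0.25 = 0.0625): 0.106 − 0.80×0.846×0.0625 = 0.106 − 0.042 = +0.063. The difference widens.

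With equal d, the sign turns where the late-risk ratio, LLTS to sham, is 0.50/0.80 = 0.625. The documents do not say on which side of this the trial lies.

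**4. Range under day-by-day assumptions.** AF risk is placed early, in line with Section 1.A (usual onset days 2 to 4, peak day 2). All other inputs are assumed.

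*Equal late hazard in both arms:* 1–3% per day from day 5, median stay 5 or 6 days, 36 per arm, read at day 10.

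- Median 5 days, 2% per day: true 49.2% v 17.0%, 1−KM 53.0% v 23.6%. The difference goes from 32.2 to 29.4 points.
- Same, with sicker patients staying longer: true 50.8% v 20.0%, 1−KM 55.7% v 29.8%. The difference goes from 30.8 to 25.9.
- Extremes: 32.6 to 31.8, and 29.6 to 22.0.
- In separate runs with true incidence fixed at 50% and 20% and equal discharge patterns, the change at day 10 was −4.7 to +0.6 points.

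*Same early set-up, hazard ratio of 0.25 kept after day 4:* the difference widened in all 12 scenarios, by 1.0 to 3.8 points (for example 34.4 to 37.1).

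*Constant hazard ratio, true incidence fixed at 0.50 v 0.20 by day 14, late hazard 5%, 20% or 40% of peak.* Change in the arm difference at day 14:

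| AF-free discharge pattern | 5% | 20% | 40% |
|---|---|---|---|
| Same in both arms (from day 4, 0.5/day) | +0.021 | +0.059 | +0.087 |
| LLTS somewhat earlier (day 3, 0.7/day v day 4, 0.5/day) | −0.005 | +0.019 | +0.029 |
| LLTS much earlier (day 3, 1.0/day v day 5, 0.3/day) | −0.032 | −0.038 | −0.060 |
| LLTS later (day 5, 0.3/day v day 4, 0.5/day) | +0.031 | +0.086 | +0.137 |

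In every scenario 1−KM was at or above the true incidence. Including an extreme case with sham patients leaving much earlier (day 3, 1.0/day v LLTS day 5, 0.3/day), the day-14 excess per arm ran from 0.014 (0.214 v 0.200) to 0.310 (0.810 v 0.500).

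**The case against.** The strongest reply is that the plan never says AF-free patients are censored at discharge. If they are carried AF-free to a fixed horizon, 1−KM equals the crude percentage and the problem disappears. That is correct. Censoring at discharge is inferred from standard practice, and what stands is that the rule is unstated and the usual default gives the wrong figure.

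Second, Section 6, where Kaplan-Meier is named, defines an outcome that continues onto the 14-day monitor. For that outcome discharge is not a competing event. This also stands, but Section 2 still makes inpatient AF primary and monitor-detected AF secondary.

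Third, the arms are compared on percentages, no log-rank test is specified, and Aim 2 speaks of incidence rather than time. None of these needs censoring, so the harm is confined to the inpatient time-to-event curve and anything read from it.

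Two stronger readings are tempting. One is that Kaplan-Meier is the only time-to-event method in the plan. Cox regression is also named, though for demographic variables and not as a competing-risk remedy. The other is that the benefit of LLTS is biased toward zero, because more LLTS patients leave AF-free. That follows only if late AF risk is similar in the arms or LLTS patients leave much earlier. Stimulation stops at 48 hours, which makes similar late risk plausible, but the documents do not establish it. They give no discharge times by arm either.

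**Conclusion.** The concern holds for the Section 2 endpoint. If inpatient AF is analysed by Kaplan-Meier with censoring at discharge, the curve overstates inpatient AF in both arms and will not match the reported percentage. That direction follows from the algebra; the amount depends on assumed hazards and discharge times.

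The effect on the arm difference has no settled sign. A shift of a few points either way is typical of the scenarios examined, with larger widening if LLTS patients leave later than sham patients. The documents therefore support neither a claim that benefit would be hidden nor one that it would be exaggerated. The point deserves correction but does not threaten the percent-incidence comparison, the sample size, or the Section 6 outcome followed through the monitor.

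**What to change.** 1. Reconcile Sections 2 and 6 so that one definition of the primary AF endpoint applies throughout.
2. For any inpatient-only AF analysis, replace Kaplan-Meier with the cumulative incidence function (Aalen-Johansen), with AF-free discharge and death without AF as competing events. Once every stay has ended, its final value equals the observed percentage with inpatient AF. Compare the arms on that incidence or with Gray's test.
3. For the Section 6 outcome, keep Kaplan-Meier. State that patients are not censored at discharge but followed through the 14-day monitor, and say how death and any gap before a mailed or collected monitor is worn are handled.

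The cost is a few sentences in Sections 2 and 6 and the synopsis, with standard software. No new data or patients are needed. The small downside is a curve less familiar to some readers.

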3. SUBJECT SELECTION AND WITHDRAWAL

Sites:

Subjects selected for study will be recruited from the University of Chicago Medical Center (Chicago, IL).

Eligibility:

Eligible patients will be all patients undergoing CABG and/or valve surgery.

Inclusion Criteria:

1. Patients ≥ 18 years of age, <90 years of age
2. Estimated life expectancy of at least 1 year at the time of enrollment
3. History of sinus rhythm or paroxysmal atrial fibrillation

Exclusion Criteria:

1. Patients ≥ 90 years of age, <18 years
2. Patients with known prior history of persistent or permanent AF
3. Atrial Fibrillation occurrence within the last 24 hours of procedure
4. Urgent or Emergency cases
5. Pregnant patients
6. Patients undergoing the following cardiac procedures: heart transplant, pulmonary thromboendarterectomy, isolated aortic arch procedures, congenital heart disease, ventricular assist device insertion, extracorporeal membrane oxygenation insertion, and surgical AF ablation
7. Antiarrhythmics prior to surgery (Class I and Class III)
8. High degree AV block requiring temporary pacing
9. MAZE procedure

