5. STUDY PROCEDURES

Pre-Stimulation:

- Patients will be screened for study
- Discomfort threshold bilaterally will be measured (20 Hz) for 5 minutes
- Pre-implant ECG reviewed (to be performed on day of screening)
- Baseline transthoracic echocardiogram (TTE) reviewed (does *not* need to be performed during inpatient hospitalization; outpatient or outside-hospital TTE report may also be performed)
- NYHA functional class to be determined by treating physician
- Operating physician will be informed of patient randomization allocation to facilitate planning of procedure

Randomization, Implant, and Periprocedure Care:

- LLTS or sham will instituted upon arrival in PACU/recovery after surgery with right sided LLTS. The site of stimulation will alternate every 4 hours between right and left tragus for total stimulation duration of 48 hours.
- Postoperative care for the cardiac surgical patient will be performed as per routine standard of care by the treating primary team
- The patient will be maintained on telemetry during the entire inpatient hospitalization
- Telemetry will be checked daily to evaluate for any new-onset AF
- Predischarge ECG will be performed at the time of hospital discharge
- The patient will be fitted with a 14-day event monitor (i.e. Zio patch or Cardionet monitor) at the time of discharge or to be mailed to the patient/picked-up by patient immediately after discharge on a weekend discharge day
- Blood will be collected for C-reactive protein measurement to assess inflammation per routine lab assessments

Follow-Up Visit (can be performed between 2 weeks and 1 month after discharge):

- The patient will return the 14-day monitor, if not already mailed back
- Routine clinical check as per primary team

Future contact:

- Patients will be asked to participate in an extended registry (protocol IRB16-0272) to evaluate longer-term clinical outcome after study completion. Patients will be asked to sign a separate consent form for participation in this study.

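### On its natural reading, Section 2 counts sustained VT or VF only when it needs an undefined device therapy; hypothesis b and Aim 2 set no such condition, and Section 6 lists no VT/VF outcome

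*Combined protocol and SAP*

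**What the plan says.** Section 1.B, hypothesis b, expects LLTS to "reduce incidence of significant ventricular arrhythmias (i.e., nonsustained or sustained VT/VF"). Aim 2 in the same section lists "incidence of nonsustained or sustained VT/VF" among the acute outcomes. Neither statement depends on how the arrhythmia is treated.

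Section 2, under the primary endpoints, words the electrocardiographic endpoint differently: "Arrhythmia occurrence (i.e., AF, nonsustained VT, VT or VF requiring device therapy"), to be documented over the whole study. The plan does not say what device therapy means.

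Section 3 sets the population: "Eligible patients will be all patients undergoing CABG and/or valve surgery". Neither the inclusion nor the exclusion list mentions having an implanted device.

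On rhythm capture, Section 5 states that "The patient will be maintained on telemetry during the entire inpatient hospitalization", and gives the purpose of the review: "Telemetry will be checked daily to evaluate for any new-onset AF".

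The primary outcomes in Section 6 are AF and a stay of more than 5 days. The secondary outcomes are AF burden, C-reactive protein, actionable AF, stroke or TIA, and mortality. No ventricular outcome appears. The sentence on comparing the strategies names POAF incidence and length of stay only. Blinded assessment is described for time to AF.

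**The concern.** The hypothesis and aim ask about one set of events and the endpoint counts a smaller one. What is left out is the more serious end of the range: a short nonsustained run is an event, but a sustained episode may not be, depending on how it was handled. A result on hypothesis b could then rest mainly on nonsustained VT and be read as a result on ventricular arrhythmia in general.

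The condition also makes the event depend on a treatment decision as well as on the rhythm. The trial is single-blind, and Section 5 has the operating physician told the allocation. A definition based on rhythm alone and read by blinded assessors avoids that dependence.

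Section 6 does not resolve the difference. It does not say which VT/VF events are compared, over what period, or who reads them.

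**Working it through.** **The plan's own figure.** The only computed figure is the sample size, and it concerns AF or a stay of more than 5 days. Inputs from Section 6: event proportions 0.50 and 0.20, two-sided alpha 0.05, power 80%, unpooled Z-test, 10% dropout.

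n per arm = (1.960 + 0.842)² × (0.5 × 0.5 + 0.2 × 0.8) / 0.30² = 35.76, rounded up to 36; 36 / 0.90 = 40 per arm, 80 in total.

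The figure reproduces. It neither supports nor weakens the present point, since no rate or size is given for VT/VF.

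**The definitions side by side.** Nonsustained VT is a separate item in the Section 2 list, so the condition is taken to apply to the last item, VT or VF. Two meanings of device therapy are possible:

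| Event | Hypothesis b and Aim 2 | Section 2, implanted device only | Section 2, external shock included |
|---|---|---|---|
| Nonsustained VT | counted | counted | counted |
| Sustained VT that ends by itself | counted | not counted | not counted |
| Sustained VT/VF treated with drugs only | counted | not counted | not counted |
| Sustained VT/VF ended by external shock | counted | not counted | counted |
| Sustained VT/VF treated by an implanted device | counted | counted | counted |

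The second and third rows differ from Aim 2 under both meanings. The fourth differs only under the implanted-device meaning. The document leans towards that meaning: ICD and CRT are in the abbreviation list, and Section 4 speaks of pacemakers and defibrillators as cardiac devices. It does not settle the matter.

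**The observation period.** Aim 2 places VT/VF among acute outcomes and gives the 14-day monitor for AF. Section 2 documents arrhythmia over the whole study. The two differ here as well.

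**What 80 patients could show.** The documents give no VT/VF rate, so this is an illustration by assumption: LLTS halves a control proportion p₂ to p₁ = p₂/2, with n = 40 per arm and the pooled two-proportion test. With p̄ the mean of p₁ and p₂,

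power = Φ{ [ |p₂ − p₁| √n − 1.96 √(2p̄(1 − p̄)) ] / √(p₁(1 − p₁) + p₂(1 − p₂)) }.

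- p₂ = 0.05, p₁ = 0.025: (0.158 − 0.527) / 0.268 = −1.37, power about 8%.
- p₂ = 0.40, p₁ = 0.20: (1.265 − 1.270) / 0.632 = −0.01, power about 50%.

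With 36 evaluable patients per arm the range is about 8% to 46%. Under these assumptions the comparison is exploratory however the outcome is worded.

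**The case against.** The strongest reply is that the plan already contains what is needed. Aim 2 names the outcome without any condition, telemetry runs for the whole stay and is full-disclosure, and Section 6 gives Fisher's exact or Chi-square for categorical variables. A comparison by arm could therefore be made. This stands against a stronger reading that a reader might infer, namely that the ventricular hypothesis cannot be tested at all. It does not say which of the two definitions would be used, and Section 6 does not list the outcome.

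A reader might also infer that VT/VF is recorded only when a device treats it. That is wrong for nonsustained VT, which is listed without the condition.

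A third inference is that patients without an implant can never contribute a sustained event, so that almost the whole cohort is lost. This needs device therapy to mean implanted-device therapy, which the text does not say, and a figure for the share of patients with a device, which the documents do not give.

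Grammatically the condition could also attach to VF alone, leaving all VT counted. Most of the gap would then close, but VF would still carry a condition that Aim 2 lacks. That the sentence allows several readings is itself a reason to reword it.

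Finally, the consequence is limited. VT/VF is outside the Section 6 primary outcomes and the sample-size composite, and death is recorded separately. This is accepted.

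**Conclusion.** The point holds as a conflict between Sections 1 and 2 together with an omission in Section 6. On the natural reading, the Section 2 endpoint leaves out sustained VT/VF that ends by itself or is treated with drugs, whichever meaning device therapy has. If the term means implanted devices, it leaves out episodes ended by external shock too. The endpoint therefore does not measure what hypothesis b and Aim 2 ask.

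The conclusion rests on the condition applying to both VT and VF. The number of events lost cannot be estimated from the documents. The main comparison and the 80 patients are unaffected. The correction is worth making before analysis because, without it, a VT/VF result would depend on a definition chosen afterwards.

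**What to change.** 1. **Section 2:** delete the device-therapy condition, so that the outcome is any nonsustained or sustained VT, or VF, however treated, as in Aim 2. State the criteria that separate nonsustained from sustained VT.
2. **Section 6:** add this as a secondary outcome, labelled exploratory. Compare the proportion of patients with at least one event per arm, using the Fisher's exact or Chi-square test already named, for the index hospitalization on full-disclosure telemetry. If Section 2 keeps the whole study as its period, report 14-day monitor events separately.
3. **Sections 5 and 6:** extend the telemetry review to VT/VF and have it read by the assessors already blinded for AF.

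The cost is a few lines of text and some extra reading time. Telemetry and monitor recordings are already made, but the described review covers AF only, so noting VT/VF is additional work. The comparison remains exploratory with 80 patients and should be reported as such.
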